14.5 Physical Examination

Physical examinations are performed at Screening Visit 1, Baseline (Week 0), and Week 4 (EOT/ET). Physical examination results (normal, abnormal, and not done) will be summarized in a frequency table by treatment group, body system and visit.

14.6 Other Safety Endpoints

Columbia-Suicide Severity Rating Scale (C-SSRS)

The C-SSRS Baseline/Screening version will be completed at the Screening visit and the version assessing information since the last visit will be completed at all following visits (including the Baseline visit).

There are 5 questions about suicidal ideation, representing 5 types of suicidal ideation: wish to be dead; non-specific active suicidal thoughts; active suicidal ideation with any methods (not plan) without intent to act; active suicidal ideation with some intent to act, without specific plan; active suicidal ideation with specific plan and intent. If a subject answers “yes” to any of these

5 questions at any post-Baseline visit including unscheduled and out of window visits, this subject will be counted as having suicidal ideation in this study.

There are 5 questions about suicidal behavior, representing 5 types of suicidal behavior: actual attempt; interrupted attempt; aborted attempt; preparatory acts or behavior; suicide. If a subject answers “yes” to any of these 5 questions at any post-Baseline visit including unscheduled and out of window visits, this subject will be counted as having suicidal behavior in this study.

Suicidality is defined as a subject who reported at least 1 occurrence of suicidal ideation or at least 1 occurrence of suicidal behavior at any post-Baseline visit including unscheduled and out of window visits.

All data will be listed. The event counts and the number and percentage of subjects reporting any post-Baseline suicidal ideation, suicidal behavior, or suicidality will be summarized by treatment group.

Movement Disorder Society-Unified Parkinson’s Disease Rating Scale (MDS-UPDRS) Part III (motor examination)

The MDS-UPDRS is a comprehensive battery of motor and behavioral indices derived from the Columbia Scale. The MDS-UPDRS Part III will be used to assess motor function and is a motor examination consisting of 18 rater based items plus Hoehn and Yahr scale (describing how the symptoms of Parkinson’s disease progress). Each item rating ranges from 0 to 4:

0: Normal; 1: Slight; 2: Mild; 3: Moderate; 4: Severe

Some of the 18 items have subitems. In these cases, the item scores are defined as the sum of the subitem scores. If any of the subitem scores are missing then the corresponding item score will be missing.

The following item scores will be derived as the sum of the Right and Left subitem scores: finger tapping, hand movements, pronation-supination movement of hands, toe tapping, leg agility, postural tremor of the hands, and kinetic tremor of the hands.

The rigidity item score is derived as the sum of the neck, right upper extremity, left upper extremity, right lower extremity, and left lower extremity subitem scores.

The rest tremor amplitude item score is derived as the sum of the lip/jaw, right upper extremity, left upper extremity, right lower extremity, and left lower extremity subitem scores.

The Hoehn and Yahr scale is a single item question that is used to assess the stage of Parkinson’s disease; the score ranges from 0 to 5:

0: Asymptomatic

1: Unilateral involvement only

- 2: Bilateral involvement without impairment of balance
- 3: Mild to moderate involvement; some postural instability but physically independent; needs assistance to recover from pull test
- 4: Severe disability; still able to walk or stand unassisted
- 5: Wheelchair bound or bedridden unless aided

The assessment is to be completed at the clinic visits at Baseline (Week 0) and Week 4 (EOT/ET).

The observed and change from Baseline values will be summarized. The change from Baseline to Week 4 in the score for each of the 18 items as well as Hoehn and Yahr Stage score will be analyzed using an ANCOVA model with treatment group as a factor and the Baseline value as a covariate. Missing data will not be imputed.

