	
Actigraphy Analyses
 
Actigraphy data on physical activity will be collected continuously using a wearable device from at least one week before the Baseline visit through Week 4. Exploratory analyses will be used to see how the data should be collapsed into average values for each time of day, day, and week. The outcome and change from Baseline in actigraphy data will be evaluated using an MMRM model. This model will include fixed effects of treatment, time of day, and day of visit, as well as the continuous fixed covariate of Baseline scores. All of these factors have naturally occurring interaction terms, which will also be included in analysis models.
 
Safety Analyses
 
The serum clinical chemistry, hematology, and urinalysis results at each time point will be summarized by treatment group. Change from Baseline values will also be summarized.
 
The number and percentage of subjects with potentially clinically important (PCI) post-Baseline laboratory values will be summarized by treatment group at each post-Baseline visit and overall post-Baseline for selected parameters. The PCI criteria will be specified in the statistical analysis plan.
 
Vital signs and body weight at Baseline and each post-Baseline visit will be summarized by treatment group. Change from Baseline values will also be summarized.
 
The results of the physical examinations at each visit will be tabulated by treatment group.
 
Electrocardiogram parameters at study visits will be summarized by treatment group. Change from Baseline values will also be summarized. Categorical analyses will be conducted on the incidence of subjects with prolonged QTc intervals and changes in QTc intervals in accordance with ICH guidelines.
 
For the C-SSRS, the number and percentage of subjects with suicidal ideation or suicidal behavior during the study will be tabulated.
 
MDS UPDRS Part III observed value and change from Baseline to Week 4 will be summarized by treatment group. The change from Baseline to Week 4 in the MDS UPDRS Part III score will be analyzed using an analysis of covariance (ANCOVA) model with treatment group as a factor and the Baseline value as a covariate.

Date	31 January 2020

Figure S-1 **Schematic of Study Design for ACP-103-056**

[figure not shown]

R=randomization

* Pre-drug actigraphy data and handheld device assessments are conducted prior to randomization (Baseline)

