9.5.3 Other Safety Analyses

The serum clinical chemistry, hematology, and urinalysis results at each time point will be summarized by treatment group. Change from Baseline values will also be summarized.

The number and percentage of subjects with potentially clinically important (PCI) post-Baseline laboratory values will be summarized by treatment group at each post-Baseline visit and overall post Baseline for selected parameters. The PCI criteria will be specified in the statistical analysis plan.

Vital signs and body weight at Baseline and each post-Baseline visit will be summarized by treatment group. Change from Baseline values will also be summarized.

The results of the physical examinations at each visit will be tabulated by treatment group.

Electrocardiogram parameters at study visits will be summarized by treatment group. Change from Baseline values will also be summarized. Categorical analyses will be conducted on the incidence of subjects with prolonged QTc intervals and changes in QTc intervals in accordance with ICH guidelines.

For the C-SSRS, the number and percentage of subjects with suicidal ideation or suicidal behavior during the study will be tabulated.

MDS UPDRS Part III observed value and change from Baseline to Week 4 will be summarized by treatment group. The change from Baseline to Week 4 in the MDS UPDRS Part III score will be analyzed using an analysis of covariance (ANCOVA) model with treatment group as a factor and the Baseline value as a covariate.

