5.2 Derived Efficacy Variables

In general, assessment total scores and subscores will be derived within the analysis datasets. In the event that total scores and/or subscores are also collected on the electronic case report from (eCRF), the derived values will be used for all analyses. Both the raw and derived scores will be presented in listings.

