12.4 Multiple Comparisons / Multiplicity

Multiplicity will not be adjusted in the analysis of exploratory efficacy endpoints due to the exploratory nature of this trial.

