19. CHANGES TO ANALYSES SPECIFIED IN PROTOCOL

Because this trial was stopped early after randomizing only 11 subjects, all of the mixed-model repeated measures analyses were changed to ANCOVA in order to minimize possible non-convergence issues.

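### SAP 14.6 replaces the protocol's single ANCOVA of the MDS-UPDRS Part III score with 19 item-level ANCOVAs, defines no Part III sum, and SAP 19 does not declare the change

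*SAP*

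**What the plan says.** Protocol 9.5.3, repeated in the synopsis, treats Part III as one measure. For description: "MDS UPDRS Part III observed value and change from Baseline to Week 4 will be summarized by treatment group". For modelling: "The change from Baseline to Week 4 in the MDS UPDRS Part III score will be analyzed using an analysis of covariance (ANCOVA) model". Treatment is the factor there, and the covariate is the Baseline value. Protocol 6.3.5 describes Part III as 18 rater-based items and does not mention Hoehn and Yahr. Protocol 2.2.1 lists Part III among the exploratory endpoints, under safety and tolerability.

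SAP 14.6 builds item scores from subitems and stops there. On missing subitems: "If any of the subitem scores are missing then the corresponding item score will be missing". The ANCOVA outcomes are "The change from Baseline to Week 4 in the score for each of the 18 items as well as Hoehn and Yahr Stage score", and the paragraph ends with "Missing data will not be imputed".

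Three other SAP texts bear on the point:
- SAP 5.2, under derived efficacy variables: "In general, assessment total scores and subscores will be derived within the analysis datasets".
- SAP 12.4: "Multiplicity will not be adjusted in the analysis of exploratory efficacy endpoints due to the exploratory nature of this trial".
- SAP 19 records one departure from the protocol: "all of the mixed-model repeated measures analyses were changed to ANCOVA".

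**The concern.** The protocol names one score, and the SAP analyses its components without ever forming that score. Two things follow.

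- The motor comparison with placebo that the protocol planned is not produced. The reader gets up to 19 separate item results instead. Some may fall below 0.05 by chance, and 14.6 defines no overall score to set them against.
- The departure cannot be traced. A reader who checks SAP 19 to see what changed will not find it. The reason given there, non-convergence of mixed models, does not apply to one ANCOVA on a sum.

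**Working it through.** **1. Is a Part III sum defined or modelled?** SAP 14.6 sums right and left ratings for seven items and five body regions for rigidity and for rest tremor. No sentence adds the 18 items. By contrast, the same SAP writes out totals for the MMSE (5.2.1) and for the PD NMS with its range and missing-item rule (5.2.8). MDS-UPDRS has no subsection in 5.2.

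**2. Number of models.** Protocol: 1. SAP: 18 + 1 = 19. If each model reports both active arms against placebo, as Protocol 9.2 foresees for exploratory endpoints, that is 2 contrasts against 19 × 2 = 38. SAP 14.6 does not say which tests will be shown. SAP 5.1 sets a default two-sided 5% level.

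**3. Is the change declared?** SAP 19 covers analyses that were MMRM in the protocol. Part III was already ANCOVA in Protocol 9.5.3, so that entry does not reach it.

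**4. What the sum would be.** From the SAP's own subitem lists: 7 × 2 + 5 + 5 + 9 single items = 33 ratings, each 0-4, giving a range of 0 to 33 × 4 = 132.

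**5. Chance findings under the null.** The documents give no figure to reproduce. If tests were independent, 1 − 0.95^19 = 62% and 1 − 0.95^38 = 86%. Items are correlated and often at zero, so a simulation gives a range. Assumptions:
- 11 subjects (SAP 19), split 3 placebo and 4/4 active, all with Baseline and Week 4 data.
- Equal correlation between items of 0 to 0.7, and Baseline-Week 4 correlation of 0.7.
- ANCOVA of change on arm and Baseline. Items with no residual variance give no test.
- 1,500 or 2,000 replicates, with Monte Carlo standard error up to 1.3 points.

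Chance of at least one p<0.05 (the range runs over the item correlation, highest at zero correlation except possibly for the sum):

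| Score shape | 19 overall tests | 38 placebo contrasts |
|---|---|---|
| Normal | 37-65% | 52-83% |
| Ratings 0-4, well spread | 36-62% | 53-81% |
| Half of ratings zero | 34-56% | 51-78% |
| 84% of ratings zero | 22-39% | 36-59% |
| 84% of item scores zero | 19-25% | 29-43% |
| One summed score | 2-6% (1 test) | 6-10% (2 contrasts) |

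With 8 completers (assumed 2 placebo, 3/3 active), the 19-test figures are 40-64% for the first three shapes and 11-34% for the two strong-floor shapes. The sum gives 4-7%.

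**6. Precision of the restored estimate.** Residual df = 11 − 3 arms − 1 covariate = 7. The 95% CI half-width in residual SDs, ignoring Baseline imbalance, is t(0.975, 7) × √(1/4 + 1/4) = 1.67 or t(0.975, 7) × √(1/4 + 1/3) = 1.81. With 8 subjects (4 df) it is t(0.975, 4) × √(1/3 + 1/3) = 2.27 or t(0.975, 4) × √(1/3 + 1/2) = 2.53.

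**7. Cost of a complete-case total.** A change score needs 33 × 2 = 66 ratings. If ratings go missing independently at an assumed 0.1% each, the loss is 1 − 0.999^66 = 6.4% of subjects (0.7 of 11). At 1% each it is 1 − 0.99^66 = 48.5% (5.3 of 11).

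**The case against.** The best defence has four parts.

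- **Exploratory testing.** Protocol 9.2 already calls testing of the exploratory endpoints exploratory, and Part III is one of them. The reason that SAP 12.4 gives for not adjusting, the exploratory nature of the trial, applies here equally; only its restriction to efficacy leaves Part III out. This stands as far as it goes. Unadjusted testing in a pilot is ordinary, and multiplicity is the secondary point. It does not supply the missing overall estimate.
- **The word total.** The protocol never says that the Part III score is a total. That is true. But one score with one Baseline covariate, from a scale described as 18 items, is most naturally the sum, and an item-by-item reading does not fit it.
- **A total may still be derived.** SAP 5.2 says that totals are generally derived, SAP 14.6 says observed values and changes will be summarized, and table specifications sit in a separate document. A descriptive total may therefore appear. The claim is accordingly limited to what 14.6 defines and models: none of these texts gives a formula or puts a total into an ANCOVA.
- **Small consequence.** With an interval of about 1.7 to 2.5 residual SDs either side, no motor-safety conclusion is possible anyway. This also stands, and it limits the gain to an interpretable, protocol-specified estimate and a traceable record.

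**Conclusion.** The concern holds. SAP 14.6 neither defines nor models a Part III sum, it turns one planned ANCOVA into 19, and SAP 19 is silent on this. All three follow from the text and need no assumption beyond reading the protocol's single score as the item sum. The simulated error rates are illustrative. They depend on an assumed arm split, completeness, item distribution and correlation, and on p-values being shown for the items. The point should be fixed but is not critical: TEAEs, the primary endpoint, are unaffected, and neither approach has useful power with 11 subjects.

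**What to change.** In SAP 14.6:

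1. Define the Part III total as the sum of the 18 item scores (33 ratings, 0-132), excluding Hoehn and Yahr.
2. Run the protocol's single ANCOVA on its change to Week 4, with 95% CIs for pimavanserin and for quetiapine against placebo.
3. Present the items and Hoehn and Yahr descriptively. If the item models are kept, label them supplementary and unadjusted, and list them in SAP 19 as an addition to the protocol.
4. State a missing-rating rule. The default that fits the present text is a missing total when any rating is missing. If the sponsor prefers proration, it should be done at rating level, because items run 0-4, 0-8 or 0-20, with the threshold fixed in advance. SAP 5.2.8 already prorates the PD NMS total alongside a no-imputation statement in SAP 12.3, so there is precedent. The no-imputation sentence in 14.6 should then be reworded so that the two do not conflict.

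The cost is SAP wording only, with no new data. The downside is the possible loss of subjects under a complete-case total: 6% or 48% at the two assumed missing rates.

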15. CLINICAL PHARMACOKINETIC AND PHARMACODYNAMIC ANALYSES

No pharmacokinetic samples are collected in this study.

16. INTERIM ANALYSIS

No interim analysis is planned in this study.

17. DATA MONITORING/REVIEW COMMITTEE

There is no data monitoring/review committee in this study.

18. COMPUTER METHODS

Statistical analyses will be performed using Version 9.4 (or newer) of SAS® on a suitably qualified and validated environment.

Validation and quality control of the tables, listings and figures containing the results of the statistical analyses will follow appropriate standard operating procedures.

19. CHANGES TO ANALYSES SPECIFIED IN PROTOCOL

Because this trial was stopped early after randomizing only 11 subjects, all of the mixed-model repeated measures analyses were changed to ANCOVA in order to minimize possible non-convergence issues.

20. APPENDICES

20.1 Summary of Version Changes

Version No:	Document History	Author(s)	Version Date
Description of Update			
1.0	Original version		19 October 2020

20.2 Supplementary Tables

Table 6 Schedule of Events and Assessments

	Screening	Baseline	Double-blind Treatment Period				Safety Follow-up
Visit Week (Study Day)	-4	0	1 (Day 7)	2 (Day 14)	3 (Day 21)	4/EOT (Day 28)	8 ¹ (Day 58)
Visit Number	1	2	3	4	5	6/ET	7
Visit window (days)	0	0	±3	±3	±3	±3	±4
Type of Visit	Clinic	Clinic	Clinic	Clinic	Clinic	Clinic	Telephone
Informed consent	X						
Inclusion/exclusion criteria	X	X					
Medical history and demographics	X						
Psychiatric and neurological history	X						
Physical examination (including neurologic examination)	X	X				X	
Training on the use of the handheld device and the actigraph ^a	X	X					
Orthostatic vital signs	X	X	X	X	X	X	
Weight and BMI ^b	X	X					X
Height	X						
12-lead ECG ^c	X	X	X	X	X	X	
Clinical laboratory tests	X	X		X			X
Pregnancy test ^d	X	X					X
Urine drug screen	X	X ^k					X
Capsule swallowing test ^e	X						
MMSE	X						
Dispense study drug ^g		X	X	X	X		
CGI-S ^f	X	X					
Trail Making Test ^f		X	X	X			X
HVLT-R ^f		X	X	X			X
Handheld device questionnaires ^h		X-----X					
Actigraphy data collection ⁱ		X-----X					
PD NMS Questionnaire ^f		X	X	X	X		
PGI-I ^f			X	X	X		X
CGI-I ^f			X	X	X		X
MDS UPDRS ^f		X					X
Subject and Informant satisfaction question			X	X	X	X	
Concomitant medications	X	X	X	X	X	X	X
C-SSRS ^{f,j}	X	X	X	X	X	X	

	Screening	Baseline	Double-blind Treatment Period				Safety Follow-up
Visit Week (Study Day)	-4	0	1 (Day 7)	2 (Day 14)	3 (Day 21)	4/EOT (Day 28)	8 ¹ (Day 58)
Visit Number	1	2	3	4	5	6/ET	7
Visit window (days)	0	0	±3	±3	±3	±3	±4
Type of Visit	Clinic	Clinic	Clinic	Clinic	Clinic	Clinic	Telephone
Assessment of adverse events	X	X	X	X	X	X	X
Study drug accountability			X	X	X	X	

Abbreviations: CGI-I=Clinical Global Impression-Improvement; CGI-S=Clinical Global Impression-Severity; C-SSRS=Columbia-Suicide Severity Rating Scale; ECG=electrocardiogram; EOT=end of treatment; ET=early termination; HVLT-R=Hopkins Verbal Learning Test-Revised; MDS UPDRS=Movement Disorders Society Unified Parkinson's Disease Rating Scale; MMSE=Mini-Mental State Examination; PD NMS=Parkinson's Disease Non-motor Symptoms; PGI-I=Patient Global Impression-Improvement

- a Training on the handheld device and actigraph may be done on the first day of Screening but must take place at least 7 days before the Baseline visit.
- b Measurement of weight and BMI are required at Screening and Baseline; measurement of weight (not BMI) is required at Week 4/EOT.
- c The ECG will be completed in triplicate at Visit 1 (Screening) and collected within an approximately 5-minute period. A single ECG tracing should be completed at all other designated visits.
- d A pregnancy test is only required for women of childbearing potential. Serum pregnancy should only be performed at Visit 1 (Screening); a urine pregnancy test should be performed at Baseline and EOT visits. If urine cannot be obtained in women of childbearing potential, a serum pregnancy test should be done.
- e Subjects will be assessed for their ability to swallow a test capsule (i.e., placebo).
- f This clinician-administered assessment should be conducted at least one hour after dosing when conducted at Weeks 1-4. The Baseline clinician-administered assessments should be conducted prior to dosing.
- g The site staff must observe the subject for a minimum of 60 minutes in the clinic after dosing. Subjects should not take study drug on the mornings of clinic visit days until instructed to do so by the site staff.
- h Baseline handheld device data will be collected during the 7-day period before the Baseline visit. Assessments completed on the handheld device should not be done on the days of clinic visits. See [Table 2](#) and [Table 3](#) for further details on the assessments for the handheld device.
- i Baseline actigraphy data will be collected during the 7-day period before the Baseline visit. The handheld device is to be brought with the subject for the clinic visits at Visit 2 (Baseline), Visit 3 (Week 1), Visit 4 (Week 2), Visit 5 (Week 3), and Visit 6 (Week 4). Site staff are to review completion of assessments on the handheld device and use of actigraph at Visit 3 (Week 1), Visit 4 (Week 2), Visit 5 (Week 3), and Visit 6 (Week 4).
- j The Baseline/Screening version of the C-SSRS will be administered at Screening, and the "Since Last Visit" version of the C-SSRS will be administered at all other designated visits.
- k Urine drug screen at Visit 2 (Baseline) can be performed at the clinical site for rapid results to qualify the subject for study drug administration or exclude the subject without dosing.
- l The safety follow-up visit is to occur 30 (±4) days after the last dose of study drug.

Table 7 Schedule of Assessments for Subjects on the Handheld Device (EMAs)

	Three Times Each Week				Weekly
	Sleep Assessments			PROMIS Cognitive Function	Satisfaction Question
	Nighttime Sleep ^b	Sleep-Related Impairment	Karolinska Sleepiness Scale (KSS)		
9 am ± 2 hours ^a	X	X	X	X	X
2 pm ± 2 hours		X	X	X	
7 pm ± 2 hours		X	X	X	

Abbreviations: PROMIS=Patient-Reported Outcomes Measurement Information System

Note: Assessments completed on the handheld device should not be done on the days of clinic visits. **It is recommended that assessments on the handheld device be done on the first, third and fifth days following clinic visits** (except Visit 6, the last visit); however, flexibility is permitted as long as assessments are completed 3 times each week.

^a Testing should be completed at least 1 hour after the daily administration of study drug. If subject does not complete morning assessment, then no assessments can be completed that day.

^b Questions related to nighttime sleep will be asked only at the morning assessment.

Table 8 Schedule of Assessments for Informants on the Handheld Device (EMAs)

	Three Times Each Week			Weekly
	Sleep Assessments		PROMIS Cognitive Function	Satisfaction Question
	Nighttime Sleep ^b	Sleep-Related Impairment		
9 am ± 2 hours ^a	X	X		X
7 pm ± 2 hours		X	X	

Abbreviations: PROMIS=Patient-Reported Outcomes Measurement Information System

Note: Assessments completed on the handheld device should not be done on the days of clinic visits. **It is recommended that assessments on the handheld device be done on the first, third and fifth days following clinic visits** (except Visit 6, the last visit); however, flexibility is permitted as long as assessments are completed 3 times each week.

^a Testing should be completed at least 1 hour after the subject's daily administration of study drug.

^b Questions related to nighttime sleep will be asked only at the morning assessment.
